Appendix 2. Primary Endpoint Derivation

Scenarios for VAS Values		Percent Change Calculated/ 20% Improvement derived?	30 mm Worsening Derived?	Effect on Primary Endpoint
Baseline	Post-baseline			
>0	>0	Calculated/derived	Derived	Not affected
0	>0	Assign % Change = blank/ 20% Improvement = NO	Derived	Not affected
0	0	Assign % Change = 0; 20% Improvement = NO	Worsening = NO	Not affected
> 0	0	Assign % Change = -100%	Worsening = NO	Not affected
Missing	Not Missing	Blank	Blank	Missing
Not Missing	Missing	Blank	Blank	Missing

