6.16.1. Patient Reported Outcomes: Visual Analogue Scales and Questionnaires

PROs, including Visual Analogue Scales (VAS) and questionnaires, are to be completed by the subject (where local language questionnaires are available) and should be recommended to be completed before any other study procedures. Please refer to schedule of assessments in [Appendix 2](#) for the time points for which all PRO assessments are to be completed.

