3.8.2. Analysis Visit Windows

The target study days for analysis visits are provided in the [Table 2](#) below:

Table 2. Target Days for Analysis Visits

Nominal Visit	Nominal Study Day/ Study Day on Active Treatment
Screening	< 1
Baseline	<=1
Week 2	15
Week 4	29
Week 8	57
Week 12	85
Week 18	127
Week 24	169/1
Week 26	183/15
Week 28	197/29
Week 32	225/57
Week 36	253/85
Week 42	295/127
Week 48	337/169
Follow-up Visit	NA

The nominal visit as recorded on the CRF will be used when data are summarized by visit.

Any data recorded under unscheduled visits will not be assigned to a particular visit or time point. However, the following exceptions will be made:

- An unscheduled visit prior to the first dosing of study drug may be included in the calculation of the baseline or screening value, if applicable
- Unscheduled visits after the first dose of study drug will be included in determining the maximum postbaseline toxicity grade in safety analyses

For subjects who prematurely discontinue from the study, early termination (ET) data will be assigned to what would have been the next scheduled visit where the respective data were scheduled to be collected. If this next scheduled visit for parameter falls on the visit after the latest performed scheduled visit as reported in the clinical database then the analysis visit is not assigned and the value is not included in the analyses.

Data collected at a follow-up visit will be summarized under a separate visit, and labeled “Follow-up Visit.”

3.8.3. Selection of Data in the Event of Multiple Records in an Analysis Visit Window

Depending on the statistical analysis method, single values may be required for each analysis window.

If multiple valid, nonmissing, continuous measurements exist in an analysis window, records will be chosen based on the following rules if a single value is needed:

- In general, the baseline value will be the last nonmissing value on or prior to the first dosing date of study drug, unless specified differently. If multiple measurements occur on the same day, the last nonmissing value prior to the time of first dosing of study drug will be considered as the baseline value. If these multiple measurements occur at the same time or the time is not available, the average of these measurements will be considered the baseline value.
- For postbaseline values:
 - The record closest to the nominal day for that visit will be selected.

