3.9. Efficacy Estimands

Three efficacy estimands: a treatment-policy estimand, a hypothetical estimand and a composite estimand, are defined for the primary and secondary efficacy endpoints.

The **treatment-policy estimand** is the primary estimand for the primary and secondary efficacy endpoints.

1) Population: Subjects in the FAS

- 2) Variable: Primary and secondary endpoints
- 3) Intercurrent events: The occurrence of an intercurrent event is irrelevant. All observed values will be used regardless of occurrence of an intercurrent event

The **hypothetical estimand** is defined as following. This is the supportive estimand for the primary and secondary efficacy endpoints.

- 1) Population: Subjects in the Full Analysis Set (FAS).
- 2) Variable: Primary and secondary endpoints
- 3) Intercurrent events: The following intercurrent events are taken into account:
 - Subject takes prohibited medication
 - Subject changes the dose of the medication required to be stable per protocol
 - Subject discontinues from study treatment

The **composite estimand** is defined as following. This is the supportive estimand for the primary and secondary efficacy endpoints.

- 1) Population: Subjects in the Full Analysis Set (FAS).
- 2) Variable: Primary and secondary endpoints
- 3) Intercurrent events: The following intercurrent events are taken into account:
 - Subject takes prohibited medication
 - Subject changes the dose of the medication required to be stable per protocol
 - Subject discontinues from study treatment

The estimators associated with each of these estimands are described in [Table 3](#) of Section 6.

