6. EFFICACY ANALYSES

Efficacy endpoints will be evaluated for the following treatment periods: placebo-controlled period up to Week 24 and the entire study up to Week 48.

The primary and secondary endpoints analyses will be based on the estimands presented in the [Table 3](#).

Table 3. Efficacy Estimands

Binary Endpoint	Treatment Policy (main)	Hypothetical	Composite
Population	FAS	FAS	FAS
Intercurrent Event	Ignore all intercurrent events	
 • Treatment discontinuation • Start of prohibited medication • The dose change of medication that is required to be stable Data after the event are treated as missing	
 • Treatment discontinuation • Start of prohibited medication • The dose change of medication that is required to be stable Data after the event are treated as no response
Main Estimator	Stratified CMH test with imputation of missing data using logistic regression	Stratified CMH test with imputation of missing data using logistic regression	Stratified CMH test with non-responder imputation of missing data

Continuous Endpoints	Treatment Policy (main)	Hypothetical	Composite
Intercurrent Event	Ignore all intercurrent events	
 • Treatment discontinuation • Start of prohibited medication • The dose change of medication that is required to be stable 	
 • Treatment discontinuation • Start of prohibited medication • The dose change of medication that is required to be stable
Main Estimator	The treatment difference will be estimated using a mixed effects model for repeated measures. Missing data will be imputed using multiple imputation	The treatment difference will be estimated using a mixed effects model for repeated measures. Missing data will be imputed using multiple imputation	The treatment difference will be estimated using a mixed effects model for repeated measures. Missing data will be imputed using multiple imputation based on observed data from the placebo group

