6.1. Multiple Imputations of Missing Data

Multiple imputation of binary variables: The MI procedure replaces each missing binary response value with a set of plausible values that represent the uncertainty about the right value to impute. Twenty imputed datasets will be generated based on logistic regression models. These multiple imputed data sets are then analyzed by using the same method for the primary analysis for complete data as specified in Section 6.3. The results from each set of imputed data sets will then be combined using Rubin's rule {Rubin 1987}. Stratification factors will be included in the imputation model.

Multiple imputation of continuous variables: All subjects with baseline measurement will be included. The MI procedure replaces each missing value with a set of plausible values that represent the uncertainty about the right value to impute. Twenty imputed datasets will be generated based on linear regression models on observed values. These multiple imputed data sets are then analyzed by using the analysis method specified in Section 6.4 for complete data. The result of each imputed data set will be combined using Rubin's rule {Rubin 1987}. Stratification factors and baseline values will be included in the imputation model as covariates.

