6.2. Definition of the Primary Efficacy Endpoint

The primary endpoint is the proportion of subjects fulfilling protocol-specified response criteria at Week 12, as compared to baseline.

Response is defined as follows (also see [Appendix 2](#)):

- For subjects with elevated hsCRP (defined as $\text{hsCRP} \geq 1.5$ upper limit of normal [ULN]) on Day 1, response is defined as achieving all of the following:
 - $\geq 20\%$ improvement in hsCRP
 - $\geq 20\%$ improvement in at least 3 out of 5 subject reported, SjS related visual analog scales (VAS; subject's assessment of global disease, pain, oral dryness, ocular dryness, and fatigue)
 - no worsening (i.e., no increase >30 mm from baseline) in any of the above VAS
- For subjects without elevated hsCRP ($\text{hsCRP} < 1.5$ ULN) on Day 1, response is defined as achieving all of the following:
 - no increase in hsCRP to ≥ 1.5 ULN
 - $\geq 20\%$ improvement in at least 3 out of 5 subject reported, SjS related VAS (subject's assessment of global disease, pain, oral dryness, ocular dryness, and fatigue)
 - no worsening (i.e., no increase >30 mm from baseline) in any of the above VAS

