6.3. Analysis for the Primary Efficacy Endpoint

6.3.1. Primary Analysis of Primary Endpoint

In the primary analysis, the primary outcome in each active treatment group will be compared to the outcome in the placebo group using a superiority test at the 2-sided 0.05-level. The following null hypotheses will be tested (vs. the respective alternative hypotheses):

- H01: There is no difference in the responder rate between filgotinib 200 mg group and placebo group at Week 12
- H02: There is no difference in the responder rate between lanraplenib 30 mg group and placebo group at Week 12
- H03: There is no difference in the responder rate between tirabrutinib 40 mg group and placebo group at Week 12

The analyses will be performed using Cochran Mantel Haenszel (CMH) test adjusted for the randomization stratification factors. If CMH test stratified by both stratification factors is not appropriate due to small cell counts then the levels of the stratification by ESSDAI scores will be pooled, and the analysis will be stratified only by use of concurrent immunomodulatory drugs at baseline. Each of the three hypotheses will be tested separately at the 2-sided, 0.05-level.

The primary analysis will be based on the Treatment Policy Estimand, with missing values imputed by multiple imputation method described in Section 6.1.

The number and percentage of responders in each treatment group as well as 95% confidence intervals (CIs) will be presented for each visit.

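### One missing VAS blanks the Week 12 primary endpoint even when the other components already decide it; imputing the components would keep that information

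*SAP*

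**What the plan says.** SAP Section 6.2 defines response at Week 12 as meeting every one of three criteria: an hsCRP criterion that depends on the Day 1 level, at least 20% improvement on at least 3 of 5 VAS, and "no worsening (i.e., no increase >30 mm from baseline) in any of the above VAS".

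SAP Appendix 2 gives the derivation for a baseline and post-baseline VAS pair. Its last two rows cover a pair with one value missing. Where the post-baseline value is the missing one, the row reads "Not Missing Missing Blank Blank Missing": percent change and worsening are left blank and the primary endpoint becomes missing. No row makes an exception for an endpoint that the other components already decide.

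SAP Section 6.3.1 bases the primary analysis on the treatment-policy estimand, "with missing values imputed by multiple imputation method described in Section 6.1". For binary variables, Section 6.1 imputes the response itself by logistic regression (20 datasets) and says of the predictors: "Stratification factors will be included in the imputation model". No VAS or hsCRP value is named as a predictor. For the supportive composite estimand, Table 3 gives "Stratified CMH test with non-responder imputation of missing data".

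**The concern.** Because response needs every criterion, one observed failure is decisive. A subject whose hsCRP criterion failed, or whose observed pain VAS rose by more than 30 mm, is a non-responder whatever the missing scale would have shown. Appendix 2 still blanks that subject, and Section 6.1 draws a response from a model that is not told about the failure. An outcome fixed by observed data is replaced by a random draw in the primary analysis.

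The per-scale reading is an inference. Appendix 2 does not say that any single missing scale is enough. However, its zero-baseline rows make sense only for one scale at a time, so this is how a programmer would most likely implement it.

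At stake are some precision in the primary comparison and, if missingness is related to the observed VAS, a small shift in the arm rates that component data could correct.

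**Working it through.** **1. The plan's own figure (context only).** SAP Section 1.3: 70% vs 30%, 2-sided 0.05, 35 per arm, 85% power. The usual two-proportion formula gives n = (1.960·√(2·0.5·0.5) + 1.036·√(0.7·0.3 + 0.3·0.7))² / 0.4² = (1.386 + 0.671)² / 0.16 ≈ 26.5, so 27 per arm. With 35 per arm, power is 93.5% (89.5% with continuity correction, 88.2% by Fisher's exact test). The stated pair is not reproduced, but 35 is on the safe side. Nothing below depends on it.

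**2. What four observed scales plus hsCRP can prove.** Each observed VAS is improved, neither, or worse by more than 30 mm; hsCRP is met or failed. That gives 2 × 3⁴ = 162 patterns.
- hsCRP failed: 81, all non-response.
- hsCRP met, at least one scale worse: 81 − 2⁴ = 65, all non-response.
- hsCRP met, none worse (16 patterns): 1 + 4 = 5 have fewer than two improved, so non-response; 6 have exactly two improved and stay open; 4 + 1 = 5 have three or four improved.

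Proven non-response: 81 + 65 + 5 = 151. In the last 5, response is proven only if the missing scale cannot have risen by more than 30 mm. On a 0-100 mm scale that means a baseline of at least 70 mm. These are logical counts, not frequencies.

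**3. Which missing value matters.** VAS are scheduled at Screening and Day 1, and under SAP Section 3.8.3 "the baseline value will be the last nonmissing value on or prior to the first dosing date of study drug". A missing baseline should be rare; the Week 12 value is the practical case.

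**4. Shares among blanked subjects (simulated).** Exactly one Week 12 VAS is missing at random. Assumed: baseline mean 50-70 mm, between-scale correlation 0.3-0.7, hsCRP failure 8-24%.

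| Arm response rate | Proven non-response | Proven response |
|---|---|---|
| 30% | 59-64% | 3-11% |
| 70% | 24-28% | 9-32% |

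**5. Numbers affected.** If 2/5/10% of 140 subjects lack one Week 12 VAS, 2.8/7.0/14.0 are blanked, and about half (1.4/3.5/7.0) are already settled.

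**6. Precision, values missing completely at random.** 4,000 simulated trials of 4 × 35; three arms at 70%, placebo at 30%; 20 imputations; stratified Mantel-Haenszel risk difference with Rubin's rules. Assumed: baseline mean 60 mm (SD 20), change SD 22 mm, correlation 0.5, hsCRP failure 16% and hsCRP always observed. Treatment is in the imputation model, although Section 6.1 does not name it (a separate matter).

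| Subjects with one VAS missing | Power, Appendix 2 | Power, components imputed | Loss (points) | Difference, Appendix 2 |
|---|---|---|---|---|
| 2% | 92.4% | 92.9% | 0.5 | 0.399 |
| 5% | 91.7% | 92.8% | 1.1 | 0.398 |
| 10% | 90.3% | 92.7% | 2.4 | 0.397 |

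With complete data, power is 92.9% and the difference 0.399. Monte Carlo error on power is about 0.3 points. A second simulation gave 91.7% vs 93.2% at 5% and 91.1% vs 94.1% at 10%, losses of 1.5 and 3.0 points. Hence the range of roughly 0.5 to 3.

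**7. Missingness related to observed VAS.** With 15% missing in the half of subjects with worse observed change and 5% in the better half, the rates targeted by binary imputation moved from 30.0% to 31.6% and from 69.9% to 70.7%. A second illustration gave 29.9% to 31.4% and 69.9% to 70.6%. The shifts are 0.7 to 1.6 points, and reversing the pattern reversed their sign.

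**8. All five VAS missing together.** Only an hsCRP failure can then settle the outcome. At 5% of subjects, 7.0 × 16% = 1.1 are settled, and power is 91.7% vs 92.2%.

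**9. Composite analysis.** Proven non-responders are scored correctly; proven responders are scored as failures. At 5% blanked: 5% × 9-32% = 0.5-1.6 points in a 70% arm (0.2-0.6 of a subject in 35), and 5% × 3-11% = 0.2-0.6 points in a 30% arm.

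**The case against.** The strongest reply is that Appendix 2 suits the imputation method chosen. If the binary response is imputed, blanking the whole endpoint is coherent under random missingness, whereas scoring only the settled cases would bias the rates. That is correct, and it is why the remedy must change the imputation and not only the table. It does not justify leaving decisive data out.

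It is also fair that the effect is small, that no rate of partial missingness is documented, and that the VAS are one schedule item which Protocol Section 6.16.1 says "should be recommended to be completed before any other study procedures". Missing all five together is therefore plausible.

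Four stronger readings are tempting and should not be drawn:
- **A conflict with SAP Section 3.9.** The sentence "All observed values will be used regardless of occurrence of an intercurrent event" stands under intercurrent events. A skipped VAS is not one, so no contradiction is shown.
- **Settled cases are mostly non-responders in every arm.** This holds in a 30% arm. In a 70% arm the ranges (24-28% and 9-32%) overlap.
- **Bias in favour of active treatment.** One proven non-responder redrawn at the planning rates adds on average 0.7/35 = 2.0 points to an active arm and 0.3/35 = 0.9 to placebo. However, the other blanked subjects are redrawn at the same marginal rate and offset this when values are missing completely at random.
- **A closed predictor list.** Section 6.1 says that the stratification factors go in; it does not say that nothing else does. The point is that the components are not named.

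**Conclusion.** The point holds as a cheap improvement, not as a threat to the primary result. Under the per-scale reading, the primary analysis discards observed components that already prove some subjects' outcomes.

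With an assumed 2-10% of subjects lacking one Week 12 VAS, the cost is roughly 0.5 to 3 points of power, with power still above 85%. There is no material bias if values are missing completely at random and treatment is in the imputation model. Arm rates shift by about 1-2 points if missingness depends on the observed VAS. The effect is near nil if the five scales go missing together. Every rate here is an assumption, and no figure is offered above 10%.

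**What to change.** For the treatment-policy and hypothetical estimands, amend four places together: the last two rows of Appendix 2, Section 6.1 (binary variables), Section 6.3.1, and the binary estimator cells of Table 3. Changing Appendix 2 alone would leave the other three prescribing binary imputation. Suggested content:

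> Missing VAS or hsCRP components are multiply imputed (20 datasets) using treatment group, stratification factors and the subject's observed VAS and hsCRP values. VAS draws are limited to 0-100 mm; hsCRP is imputed on the log scale. Response is derived in each completed dataset.

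Prespecify a reduced predictor set in case the model does not converge, for example treatment, strata, the same scale's baseline and the mean of the observed Week 12 VAS. Response is still derived from the components, so settled outcomes stay settled. A sparser set (treatment, strata and the same measure's other value) moved the difference from 0.399 to 0.402 with 10% blanked, which is a reason to keep the Week 12 summary. The suggested set itself has not been simulated.

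Do not fix the settled cases and impute the rest as a binary response, because the open cases are enriched for responders. With mid-range shares, a 30% arm has 100 − 62 − 6 = 32% open, of which (30 − 6)/32 = 75% are responders; a 70% arm has 100 − 26 − 19 = 55% open, of which (70 − 19)/55 = 93% are. With 10% blanked, that shortcut lowered the rates from 70.1% to 68.8% and from 30.2% to 28.8%.

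For the composite estimand, keep non-responder imputation, with one exception: a subject with no intercurrent event whose observed components prove response counts as a responder.

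The cost is a SAP text change before the Week 24 unblinding, plus specifying, programming and validating a larger imputation model with about 35 subjects per arm. No new data are needed.

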Appendix 3. EULAR Sjögren’s Syndrome Disease Activity Index (ESSDAI)

Promoted by European League Against Rheumatism (EULAR), the EULAR Sjögren's syndrome (SjS) disease activity index (ESSDAI) is a systemic disease physician-reported activity index that was designed to measure disease activity in patients with primary SjS. The ESSDAI is now used in multiple clinical trials as primary outcome measure.

In total, twelve organ-specific domains contributing to disease activity were identified. Each domain is divided into 3–4 levels of activity.

Domain	Activity Level	Description
Constitutional Exclusion of fever of infectious origin and voluntary weight loss	No = 0	Absence of the following symptoms
	Low = 3	Mild or intermittent fever (37.5°–38.5°C)/night sweats and/or involuntary weight loss of 5 to 10% of body weight
	Moderate = 6	Severe fever (>38.5°C)/night sweats and/or involuntary weight loss of >10% of body weight
Lymphadenopathy and lymphoma Exclusion of infection	No = 0	Absence of the following features
	Low = 4	Lymphadenopathy ≥ 1 cm in any nodal region or ≥ 2 cm in inguinal region
	Moderate = 8	Lymphadenopathy ≥ 2 cm in any nodal region or ≥ 3 cm in inguinal region, and/or splenomegaly (clinically palpable or assessed by imaging)
	High = 12	Current malignant B-cell proliferative disorder
Glandular Exclusion of stone or infection	No = 0	Absence of glandular swelling
	Low = 2	Small glandular swelling with enlarged parotid (≤ 3 cm), or limited submandibular (>2 cm) or lachrymal swelling (>1 cm)
	Moderate = 4	Major glandular swelling with enlarged parotid (> 3 cm), or important submandibular or lachrymal swelling
Articular Exclusion of osteoarthritis	No = 0	Absence of currently active articular involvement
	Low = 2	Arthralgias in hands, wrists, ankles and feet accompanied by morning stiffness (>30 min)
	Moderate = 4	1 to 5 (of 28 total count) synovitis
	High = 6	≥ 6 (of 28 total count) synovitis

Cutaneous Rate as “No activity” stable long lasting features related to damage	No = 0	Absence of currently active cutaneous involvement
	Low = 3	Erythema multiforma
	Moderate = 6	Limited cutaneous vasculitis, including urticarial vasculitis, or purpura limited to feet and ankle, or subacute cutaneous lupus
	High = 9	Diffuse cutaneous vasculitis, including urticarial vasculitis, or diffuse purpura, or ulcers related to vasculitis
Pulmonary Rate as “No activity” stable long lasting features related to damage, or respiratory involvement not related to the disease (tobacco use etc.)	No = 0	Absence of currently active pulmonary involvement
	Low = 5	Persistent cough or bronchial involvement with no radiographic abnormalities on radiography Or radiological or HRCT evidence of interstitial lung disease with: No breathlessness and normal lung function test.
	Moderate = 10	Moderately active pulmonary involvement, such as interstitial lung disease shown by HRCT with shortness of breath on exercise (NHYA II) or abnormal lung function tests restricted to: 70% >DL ≥ 40% or 80% >FVC ≥ 60%
	High = 15	Highly active pulmonary involvement, such as interstitial lung disease shown by HRCT with shortness of breath at rest (NHYA III, IV) or with abnormal lung function tests: DL < 40% or FVC < 60%
Renal Rate as “No activity” stable long lasting features related to damage, and renal involvement not related to the disease. If biopsy has been performed, please rate activity based on histological features first	No = 0	Absence of currently active renal involvement with proteinuria < 0.5 g/d, no hematuria, no leucocyturia, no acidosis, or long-lasting stable proteinuria due to damage
	Low = 5	Evidence of mild active renal involvement, limited to tubular acidosis without renal failure or glomerular involvement with proteinuria (between 0.5 and 1 g/d) and without hematuria or renal failure (GFR ≥ 60 ml/min)
	Moderate = 10	Moderately active renal involvement, such as tubular acidosis with renal failure (GFR < 60 ml/min) or glomerular involvement with proteinuria between 1 and 1.5 g/d and without hematuria or renal failure (GFR ≥ 60 ml/min) or histological evidence of extra-membranous glomerulonephritis or important interstitial lymphoid infiltrate
	High = 15	Highly active renal involvement, such as glomerular involvement with proteinuria > 1.5 g/d or hematuria or renal failure (GFR < 60 ml/min), or histological evidence of proliferative glomerulonephritis or cryoglobulinemia related renal involvement

Muscular Exclusion of weakness due to corticosteroids	No = 0	Absence of currently active muscular involvement
	Low = 6	Mild active myositis shown by abnormal EMG, MRI* or biopsy with no weakness and creatine kinase ($N < CK \leq 2N$)
	Moderate = 12	Moderately active myositis proven by abnormal EMG , MRI* or biopsy with weakness (maximal deficit of 4/5), or elevated creatine kinase ($2N < CK \leq 4N$),
	High = 18	Highly active myositis shown by abnormal EMG, MRI* or biopsy with weakness (deficit $\leq 3/5$) or elevated creatine kinase ($>4N$)
PNS Rate as “No activity” stable long lasting features related to damage or PNS involvement not related to the disease	No = 0	Absence of currently active PNS involvement
	Low = 5	Mild active peripheral nervous system involvement, such as pure sensory axonal polyneuropathy shown by NCS or trigeminal (V) neuralgia
	Moderate = 10	Moderately active peripheral nervous system involvement shown by NCS, such as axonal sensory-motor neuropathy with maximal motor deficit of 4/5, pure sensory neuropathy with presence of cryoglobulinemic vasculitis, ganglionopathy with symptoms restricted to mild/moderate ataxia, inflammatory demyelinating polyneuropathy (CIDP) with mild functional impairment (maximal motor deficit of 4/5 or mild ataxia), Or cranial nerve involvement of peripheral origin (except trigeminal (V) neuralgia)
	High = 15	Highly active PNS involvement shown by NCS, such as axonal sensorymotor neuropathy with motor deficit $\leq 3/5$, peripheral nerve involvement due to vasculitis (mononeuritis multiplex etc.), severe ataxia due to ganglionopathy, inflammatory demyelinating polyneuropathy (CIDP) with severe functional impairment: motor deficit $\leq 3/5$ or severe ataxia
CNS Rate as “No activity” stable long lasting features related to damage or CNS involvement not related to the disease	No = 0	Absence of currently active CNS involvement
	Moderate = 10	Moderately active CNS features, such as cranial nerve involvement of central origin, optic neuritis or multiple sclerosis-like syndrome with symptoms restricted to pure sensory impairment or proven cognitive impairment
	High = 15	Highly active CNS features, such as cerebral vasculitis with cerebrovascular accident or transient ischemic attack, seizures, transverse myelitis, lymphocytic meningitis, multiple sclerosis-like syndrome with motor deficit.

Hematological For anemia, neutropenia, and thrombopenia, only auto-immune cytopenia must be considered Exclusion of vitamin or iron deficiency, drug-induced cytopenia	No = 0	Absence of auto-immune cytopenia
	Low = 2	Cytopenia of auto-immune origin with neutropenia (1000 < neutrophils < 1500/mm ³), and/or anemia (10 < hemoglobin < 12 g/dl), and/or thrombocytopenia (100,000 < platelets < 150,000/mm ³) Or lymphopenia (500 < lymphocytes < 1000/mm ³)
	Moderate = 4	Cytopenia of auto-immune origin with neutropenia (500 ≤ neutrophils ≤ 1000/mm ³), and/or anemia (8 ≤ hemoglobin ≤ 10 g/dl), and/or thrombocytopenia (50,000 ≤ platelets ≤ 100,000/mm ³) Or lymphopenia (≤500/mm ³)
	High = 6	3 Cytopenia of auto-immune origin with neutropenia (neutrophils < 500/mm ³), and/or anemia (hemoglobin < 8 g/dl) and/or thrombocytopenia (platelets <50,000/mm ³)
Biological	No = 0	Absence of any of the following biological feature
	Low = 1	Clonal component and/or hypocomplementemia (low C4 or C3 or CH50) and/or hypergammaglobulinemia or high IgG level between 16 and 20 g/L
	Moderate = 2	Presence of cryoglobulinemia and/or hypergammaglobulinemia or high IgG level > 20 g/L, and/or recent onset hypogammaglobulinemia or recent decrease of IgG level (<5 g/L)

CIDP= chronic inflammatory demyelinating polyneuropathy; CK= creatine kinase; CNS= central nervous system; DLCO= diffusing CO capacity; EMG= electromyogram; FVC= forced vital capacity; GFR= glomerular filtration rate; Hb= hemoglobin; HRCT= high-resolution computed tomography; IgG= immunoglobulin G; NCS= nerve conduction studies; NHYA= New York heart association classification; Plt= platelet; PNS=peripheral nervous system

The ESSDAI overall score is obtained by addition of the twelve domain scores. The maximum theoretical ESSDAI score is 123. Usually, the score does not exceed 50.

